11.4.2.2. Treatment States for AE Data

For adverse events (AEs), treatment state will be defined as:

Treatment State	Definition
Pre-Treatment	AE Start Date < Study Treatment Start Date
On-Treatment	If AE onset date is on or after treatment start date & on or before treatment stop date +1. Study Treatment Start Date ≤ AE Start Date ≤ Study Treatment Stop Date + 1
Post-Treatment	If AE onset date is after the treatment stop date + 1. AE Start Date > Study Treatment Stop Date + 1
Onset Time Since 1 st Dose (Days)	If Treatment Start Date > AE Onset Date = AE Onset Date - Treatment Start Date If Treatment Start Date ≤ AE Onset Date = AE Onset Date - Treatment Start Date + 1 Missing otherwise.
Onset Time Since Last Dose (Days)	If Treatment Stop Date + 1 ≤ AE onset date: AE onset date – treatment stop date + 1 If Treatment Stop Date + 1 > AE onset date: AE onset date – treatment stop date Missing otherwise.
Duration (Days)	AE Resolution Date/AE End Date – AE Onset Date + 1

NOTES:

- If the study treatment stop date is missing then any AEs with a start date on or after study treatment start date will be considered to be On-Treatment.
- In the case of a completely missing AE start date, the event will be considered to have started on-treatment unless an end date for the AE is provided which is before start of investigational product; in such a case the AE is assigned as pre-treatment.

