11.6. Appendix 6: Derived and Transformed Data

11.6.1. General

Multiple Measurements at One Time Point

 • Three pre-dialysis measurements and three post-dialysis measurements of SBP, DBP and HR will be recorded at each study-specified visit. Mean of the measurements will be calculated and used in any derivation of summary statistics but if listed, all data will be presented. • After window assignment, if there are two or more values within a time window, the algorithm described in Section 11.3.2 will be followed. • Subjects having both High and Low values for Normal Ranges at any post-baseline visits for safety parameters will be counted in both the High and Low categories of “Any visit post-baseline” row of related summary tables. This will also be applicable to relevant Potential Clinical Importance summary tables.
Study Day

 • Calculated as the number of days from randomisation date : 
 • Ref Date = Missing → Study Day = Missing • Ref Date < Randomisation Date → Study Day = Ref Date – Randomisation Date • Ref Date ≥ Randomisation Date → Study Day = Ref Date – (Randomisation Date) + 1
Randomization Date

 • Date subject was randomized
Treatment Start Date

 • The date of first dose of study treatment
Treatment Stop Date

 • Calculated as the date of final dose of study treatment received. If treatment stop date is missing, then, for purposes of calculating exposure, it will be imputed using the date of last visit or the recorded date of withdrawal/completion, whichever is earlier. Note that the follow-up visit date must not be used as the date of last visit or recorded date of withdrawal/completion because this date will be off-treatment.
Study Completion/Withdrawal Date

 • Date of withdrawal for subjects withdrawing (i.e., subjects who actively withdraw or are deemed lost to follow-up) from study or date of completion of study for subjects who complete the study, as documented in the eCRF. 
 • Note: Subjects who die while on study are considered as having completed the study
Time Definitions (per GSK standard principles)

 • 1 week = 7 days • 1 month = 30.4375 days • 1 year = 365.25 days

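### SAP 11.4.2.2: the rule for AE onset since last dose gives 0 on the last-dose day and 2 on the next day, so the value 1 can never occur

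*SAP*

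**What the plan says.** The table in SAP 11.4.2.2 defines AE treatment state and three derived times, one of which is onset time since the last dose. It has two branches:

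- For onsets from the day after the final dose, the rule reads "If Treatment Stop Date + 1 ≤ AE onset date: AE onset date – treatment stop date + 1".
- For all earlier onsets, with the final-dose day among them, no 1 is added: "If Treatment Stop Date + 1 > AE onset date: AE onset date – treatment stop date".

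The reference date is the treatment stop date, which SAP 11.6.1 defines as follows: "Calculated as the date of final dose of study treatment received".

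The row above, for onset since the first dose, also has two branches, but they divide at the reference date itself. For onsets from the first-dose day, the rule reads "If Treatment Start Date ≤ AE Onset Date = AE Onset Date - Treatment Start Date + 1". For onsets before that day it takes the plain difference between onset and start date.

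The Study Day rule in SAP 11.6.1 has the same form as the first-dose rule. Dates on or after randomisation are the difference plus 1, and earlier dates are the plain difference.

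The same table sets the on-treatment window for AEs from the dates directly: "Study Treatment Start Date ≤ AE Start Date ≤ Study Treatment Stop Date + 1".

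**The concern.** In the first-dose and Study Day rules, adding 1 makes the reference day count as day 1. That works because the branch containing the added 1 begins on the reference day. In the last-dose rule this branch begins one day later, so the last-dose day falls in the plain-difference branch and gets 0, while the following day still gets the added 1.

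The result is neither a count that starts at day 1 nor a count of elapsed days. Two AEs that start on consecutive calendar days, one on the last-dose day and one on the day after, are recorded as two days apart.

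Events can fall in this range. Completers take their last dose at Day 29 (protocol 4.2). AEs are collected until the follow-up visit (protocol 7.4.1.1), which is 14 ± 3 days after treatment ends. At stake is the internal consistency of one derived safety variable and its comparability with its first-dose counterpart.

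**Working it through.** The plan states no numerical result for this derivation, so there is no figure to reproduce. The check is to apply each rule as printed.

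**Inputs**

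- Last-dose rule (SAP 11.4.2.2): onset − stop + 1 if stop + 1 ≤ onset; onset − stop if stop + 1 > onset.
- First-dose rule (SAP 11.4.2.2): onset − start if start > onset; onset − start + 1 if start ≤ onset.
- Stop date (SAP 11.6.1): the date of the final dose.
- AE treatment state (SAP 11.4.2.2): on-treatment through stop + 1, post-treatment after that.

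**Last-dose rule, with stop date = Day 29**

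- Onset Day 28: 30 > 28, so 28 − 29 = −1.
- Onset Day 29: 30 > 29, so 29 − 29 = 0.
- Onset Day 30: 30 ≤ 30, so 30 − 29 + 1 = 2.
- Onset Day 31: 30 ≤ 31, so 31 − 29 + 1 = 3.

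**Comparison.** The first column is the onset day minus the reference date, which is the stop date, or the start date for the first-dose rule. Option A branches on the stop date, as the first-dose rule branches on the start date. Option B is onset − stop for every AE. Treatment state is relative to the stop date, for onsets not before treatment start.

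| Offset (days) | Last-dose rule as written | First-dose rule | Option A | Option B | AE state |
|---|---|---|---|---|---|
| −2 | −2 | −2 | −2 | −2 | On |
| −1 | −1 | −1 | −1 | −1 | On |
| 0 | 0 | 1 | 1 | 0 | On |
| +1 | 2 | 2 | 2 | 1 | On |
| +2 | 3 | 3 | 3 | 2 | Post |
| +3 | 4 | 4 | 4 | 3 | Post |

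**Reading the table**

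- The written rule has one break, between the last-dose day (0) and the next day (2). From the day before to the last-dose day it is continuous (−1 to 0).
- The first-dose rule also has a step of 2 (−1 to 1), but that is the ordinary effect of having no day 0. A step alone is not the fault. The fault is that the last-dose rule keeps day 0 and drops day 1, which mixes two counts.
- Option A differs from the written rule in one row only, offset 0, where 0 becomes 1.
- Option B differs in every row after the last dose, each lower by 1.

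**The case against.** Four defences can be offered for the rule itself.

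- *The branch follows the on-/post-treatment boundary.* It does not. An AE on stop date + 1 is on-treatment under the same table, yet it takes the branch with the added 1.
- *The first branch means onset − (stop + 1).* Then the last-dose day and the next day would both get 0, so the rule would still be faulty. The parallel notation in the first-dose rule also favours the plain reading.
- *The text was damaged in conversion from PDF.* Both branches are complete, legible and mutually exclusive.
- *It is corrected elsewhere.* No other section of the SAP does so.

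The stronger objection is about consequence, and it largely stands. A reader might infer that the variable feeds judgements of drug relatedness. The documents do not say so. Protocol 12.5.5 has the investigator assess causality by clinical judgement. Temporal relationship is one consideration, and for an SAE the assessment comes before the first transmission to the sponsor. AEs of special interest are identified by the safety review team's blinded review of AEs during the study (SAP 11.14.8, note to Table 3.18). Neither process is described as using this derivation.

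Nor do the AE displays listed in SAP 11.14.8 and 11.14.12 name onset since last dose. Their notes mention treatment state. The variable may sit in a listing shell, but the shells are not in the text available for review. SAP 11.7.2.2 refers to calculating time to onset without saying from which dose, and it allows partial AE start dates to be imputed, so some onset days are themselves approximate.

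A reader might also infer that every post-therapy AE carries a wrong value. That depends on the convention chosen. Under the convention of the SAP's other two rules, the values after the last dose are already right and only the last-dose day is wrong. Under an elapsed-day count it is the reverse.

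**Conclusion.** The rule is wrong as written. It cannot produce the value 1, and it matches neither the first-dose rule beside it nor the Study Day rule. This rests only on the printed text and on the stop date being the date of the final dose.

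The point is minor. The discrepancy is one day in one derived timing variable. Measured against the SAP's own convention, it affects AEs that start on the last-dose day and no others. AE treatment state is set from dates directly, so the on-therapy and post-therapy AE tables and their counts are unaffected. The Day 29 hemoglobin analysis does not use the variable. How many AEs would be affected is unknown, because the documents give no AE counts by onset day.

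The documents do not show how the discrepancy arose, and the conclusion does not depend on it.

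**What to change.** In SAP 11.4.2.2, branch the last-dose rule on the treatment stop date: if AE onset is on or after the stop date, use onset − stop + 1; otherwise use onset − stop. This gives −1, 1, 2, 3 for the day before, the day of, and the first and second days after the last dose. It matches the first-dose and Study Day rules and changes only the last-dose-day value, from 0 to 1.

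The plain difference, onset − stop, for all AEs would also be consistent (−1, 0, 1, 2). It would lower every value after the last dose by one day and would leave the variable on a different convention from the SAP's other two rules, so the first option is preferable.

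Either change is one line of SAP text and one line of derivation code. No other planned analysis needs to change. If the variable appears in a listing, a footnote stating the convention would help the reader.

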11.4.2.3. Classification of Prior, concomitant, an Post-Therapy Medications

Prior medications are those taken (i.e., started) before the start date of study treatment. Concomitant medications are those taken (i.e., started or continued) at any time between the start date and stop date of study treatment, inclusive. Prior medications that were continued during the study treatment period are also considered as concomitant medications. Post-treatment medications are those started after the stop date of study treatment. Concomitant medications that were continued after the stop date of the study treatment are also considered as post-treatment medications.

It will be assumed that medication has been taken on the date in which it is reported as started or stopped. Also, for any medication starting on the same date as study treatment, it will be assumed that the medication was taken after the subject started taking the study treatment.

[Table 12](#) below illustrates how a medication is classified as prior, concomitant, or post-treatment.

Table 12 Prior, Concomitant, and Post-treatment Classification of Medications

	Pre-treatment	On-treatment		Post-treatment		Prior	Conco- mitant	Post		
(a)	x-----x	Study Treatment Start Date		Study Treatment Stop Date			Y	N	N	
(b)	x-----							Y	Y	N
(c)	x-----							Y	Y	Y
(d)					x-----x			N	Y	N
(e)					x-----			N	Y	Y
(f)								N	N	Y
(g)	?-----x							Y	N	N
(h)	?-----							Y*	Y	N
(i)	?-----							Y*	Y*	Y
(j)	x-----							Y	Y**	Y**
(k)					x-----			N	Y	Y**
(l)								N	N	Y
(m)	?-----							Y***	Y***	Y***
(n)	x-----	x				Y	Y	N		
(o)	?-----	x				Y*	Y	N		
(p)		x				N	Y	N		
(q)		x				N	Y	N		
(r)				x		N	Y	Y		
(s)				x		N	Y	Y**		
(t)					x	N	N	Y		
(u)					x	N	N	Y		
(v)			x-----		x	N	Y	Y		

1. x = start/stop date of medication
2. ? = missing start/stop date of medication
3. * If a medication is stopped On-treatment or Post-treatment and no start date is recorded it will be assumed that the medication was ongoing from the Pre-treatment phase
4. ** If a medication is started Pre-treatment or On-treatment and no stop date is recorded then usage will be assumed to be ongoing for the remainder of the study
5. *** If a medication has no start and stop date it will be assumed that the medication was ongoing from the Pre-treatment phase to the Post-treatment phase

11.5. Appendix 5: Data Display Standards & Handling Conventions

11.5.1. Study Treatment & Sub-group Display Descriptors

Treatment Group Descriptions			
PPD Randomization System		Data Displays for Reporting ^{[3][4]}	
Code	Description	Description	Order ^[1]
1	10 mg GSK1278863 three-times weekly	Dapro 10 mg ^[2]	2
2	15 mg GSK1278863 three-times weekly	Dapro 15 mg ^[2]	3
3	25 mg GSK1278863 three-times weekly	Dapro 25 mg ^[2]	4
4	30 mg GSK1278863 three-times weekly	Dapro 30 mg ^[2]	5
5	Placebo three-times weekly	Placebo	1

NOTES:

- Order represents treatments being presented in TFL, as appropriate.
- When display space is limited, 10 mg, 15 mg, 25 mg, and 30 mg can used as the description under an overall column/row title, "Dapro".
- "Dapro Total" will be used as the description when the four Daprodustat groups are pooled.
- "Total" will be used as the description when the five treatment groups are pooled.

11.5.2. Baseline Definition & Derivations

11.5.2.1. Baseline Definitions

For Hgb the average of Hgb measured by the central lab, Quest, at Week -2 and Day 1 visits will serve as the baseline value. If an unscheduled Hgb value is taken pre-treatment then this will be slotted following the algorithm in Section 11.3.1 and Section 11.3.2.

Vital signs will be measured both pre-dialysis and post-dialysis. The baseline values for vital signs will be defined as:

Pre-dialysis baseline = vital sign value obtained pre-dialysis on Day 1

Post-dialysis baseline = vital sign value obtained post-dialysis at Week -2

Weight baseline= post-dialysis weight measured at Week -2.

Unless stated otherwise, the baseline value for all other lab parameters and ECG are defined as the last pre-treatment value observed. This is generally expected to be from the Day 1 visit (except for Folate, B12 and ECG, which are only measured at Week -4), although such values may be missing or unscheduled assessments may be performed before treatment start.

Parameter	Study Assessments Considered As Baseline			Baseline Used in Data Display
	Week -4	Week -2	Day 1 (Pre-Dose)	
Safety				
Vital Signs		X	X	See description above [1]
ECG	X			Week -4
Laboratory (clinical chemistry and hematology)		X	X	Day 1
Folate, Vitamin B12	X			Week -4
Ferritin, Transferrin, Total Iron, UIBC	X		X	Day 1
Efficacy				
Hgb		X	X	Mean (Quest) See description above
PK/PD				
PK Plasma, EPO & VEGF, Hepcidin			X	Day 1

NOTES:

- Three measurements of SBP, DBP and HR will be recorded at each study-specified visit and the mean of the replicate assessments will be used as the baseline value.

11.5.2.2. Derivations and Handling of Missing Baseline Data

Definition	Reporting Details
Change from Baseline	= Post-Dose Visit Value – Baseline
% Change from Baseline	= 100 x [(Post-Baseline Visit Value – Baseline) / Baseline]
Maximum Change from Baseline	= Calculate the change from baseline at each given post-baseline timepoint and determine the maximum change

NOTES :

- Unless otherwise specified, the baseline definitions specified in Section 11.5.2.1 Baseline Definitions will be used for derivations for endpoints / parameters and indicated on summaries and listings.
- Unless otherwise stated, if baseline data is missing no derivation will be performed and will be set to missing.
- For this study %Change from Baseline (without log transformation) will be calculated only for “Absolute Reticulocyte Count.”

Some lab parameters will be log-transformed and percent change from baseline will be reported for these parameters: Hepcidin, Transferring Saturation, and VEGF.

To calculate a geometric mean for baseline measurement or at a specified timepoint, the following steps are used:

- Log-transform the data points

2. Calculate the mean and standard error (SE) of the log-transformed data
3. Exponentiate the mean, (if required, the mean – SE, mean + SE) and the endpoints of the confidence interval back to the original scale in order to obtain the geometric mean, (the geometric mean – SE, the geometric mean + SE) and the confidence interval for the geometric mean.
4. Coefficient of variation will be calculated as

$$CV = \sqrt{\exp(\text{Var}_{\log_{scale}}) - 1} \times 100\%$$

To calculate a geometric mean for the ratio of a specific timepoint to baseline (expressed as a percent change from baseline), the following steps are used:

1. Log-transform the data at both the baseline and the specified timepoint
2. For each subject, calculate a change from baseline using the log-transformed data
3. Calculate the mean and standard error (SE) of the log-transformed data
4. Exponentiate the mean, (if required, the mean – SE, the mean + SE) and the endpoints of the confidence interval, back to the original scale and then subtract 1, then multiply everything by 100% in order to express the geometric mean, (the geometric mean – SE, the geometric mean + SE) and the confidence interval (CI) as the percent change from baseline.

So, geometric mean for percent change from baseline =

$$[\text{Exp}(\sum \{ \log(\text{value at specified time point}_i) - \log(\text{baseline value}_i) \} / n) - 1] \times 100,$$

Where i = subject, n= total number of subjects, and \sum represents the sum over all subjects.

To calculate the minimum, median and maximum for the ratio of a specific timepoint to baseline (expressed as a percent change from baseline), the following steps are used:

1. Log-transform the data at both the baseline and the specified timepoint
2. For each subject, calculate a change from baseline using the log-transformed data
3. Calculate the minimum (median and maximum) of change from baseline using the log transformed data.
4. Exponentiate the minimum (median and maximum), back to the original scale and then subtract 1, then multiply everything by 100% in order to express the minimum (median and maximum) as the percent change from baseline.

So, minimum percent change from baseline =

$$[\text{Exp}(\min \{ \log(\text{value at specified time point}_i) - \log(\text{baseline value}_i) \}) - 1] \times 100,$$

Where i = subject.

11.5.3. Reporting Process & Standards

Reporting Process	
Software	

 The currently supported versions of SAS software, version 9.3. or higher will be used for all analyses unless otherwise specified. Additionally, R version 3.1.1 or higher may be used, if necessary, for analysis and the production of graphics. 	
Reporting Area	
HARP Server	: UK1SALX00175
HARP Area	: /arenv/arprod/gsk1278863/mid204836/final/
QC Spreadsheet	: /arenv/arprod/gsk1278863/mid204836/final/qc/
Analysis Datasets	

 Analysis datasets will be created according to CDISC standards (SDTM IG Version 3.1.3 & ADaM IG Version 1.1). 	
Generation of RTF Files	

 RTF files will be generated. 	
Reporting Standards	
General	

 The current GSK Integrated Data Standards Library (IDSL) will be applied for reporting, unless otherwise stated: 
 4.03 to 4.23: General Principles 5.01 to 5.08: Principles Related to Data Listings 6.01 to 6.11: Principles Related to Summary Tables 7.01 to 7.13: Principles Related to Graphics 	
Formats	

 GSK IDSL Statistical Principles (5.03 & 6.06.3) for decimal places (DP's) will be adopted for reporting of data based on the raw data collected. Numeric data will be reported at the precision collected on the eCRF. The reported precision from non eCRF sources will follow the IDSL statistical principles but may be adjusted to a clinically interpretable number of DP's. 	
Planned and Actual Time	

 Reporting for tables, figures and formal statistical analyses : 
 Planned time relative to dosing will be used in figures, summaries, statistical analyses and calculation of any derived parameters, unless otherwise stated. The impact of any major deviation from the planned assessment times and/or scheduled visit days on the analyses and interpretation of the results will be assessed as appropriate. Reporting for Data Listings: 
 Planned and actual time relative to study drug dosing will be shown in listings (Refer to IDSL Statistical Principle 5.05.1). Unscheduled or unplanned readings will be presented within the subject's listings. 	
Unscheduled Visits	

 Unscheduled visits (including early withdrawal visit) will be included in summary tables after 	

Reporting Standards	

they are slotted to the planned visits, as described in Section 11.3.1.
 
 Assessments at unscheduled visits will be included for 'any time on-treatment' time points and any time post-treatment, and in data listings, as well any algorithms that make use of additional data, as described in Section 11.3.1. Unscheduled visits will be included in figures after they are slotted to the planned visits, as described in Section 11.3.1. All unscheduled visits will be included in listings. 	
Descriptive Summary Statistics	
Continuous Data	Refer to IDSL Statistical Principle 6.06.1
Categorical Data	N, n, frequency, %
Graphical Displays	

 Refer to IDSL Statistical Principals 7.01 to 7.13. Y-axis breaks will be implemented in order to best show the distribution of values in the y-dimension. GSK Study PHI113747 figures will provide examples of the y-axis break levels, and clinical scientist review feedback will be provided on proposed y-axis breaks positions at the Dry Run Review. SAS goptions will be set to provide hardware fonts wherever possible. A color scheme will be established that is similar to that used for GSK Study PHI113747 (e.g., Orange for daprodustat, Blue for Placebo). GSK Programming will work with PPD programming to establish default SAS goptions. 	

11.6. Appendix 6: Derived and Transformed Data

11.6.1. General

Multiple Measurements at One Time Point

 • Three pre-dialysis measurements and three post-dialysis measurements of SBP, DBP and HR will be recorded at each study-specified visit. Mean of the measurements will be calculated and used in any derivation of summary statistics but if listed, all data will be presented. • After window assignment, if there are two or more values within a time window, the algorithm described in Section 11.3.2 will be followed. • Subjects having both High and Low values for Normal Ranges at any post-baseline visits for safety parameters will be counted in both the High and Low categories of “Any visit post-baseline” row of related summary tables. This will also be applicable to relevant Potential Clinical Importance summary tables.
Study Day

 • Calculated as the number of days from randomisation date : 
 • Ref Date = Missing → Study Day = Missing • Ref Date < Randomisation Date → Study Day = Ref Date – Randomisation Date • Ref Date ≥ Randomisation Date → Study Day = Ref Date – (Randomisation Date) + 1
Randomization Date

 • Date subject was randomized
Treatment Start Date

 • The date of first dose of study treatment
Treatment Stop Date

 • Calculated as the date of final dose of study treatment received. If treatment stop date is missing, then, for purposes of calculating exposure, it will be imputed using the date of last visit or the recorded date of withdrawal/completion, whichever is earlier. Note that the follow-up visit date must not be used as the date of last visit or recorded date of withdrawal/completion because this date will be off-treatment.
Study Completion/Withdrawal Date

 • Date of withdrawal for subjects withdrawing (i.e., subjects who actively withdraw or are deemed lost to follow-up) from study or date of completion of study for subjects who complete the study, as documented in the eCRF. 
 • Note: Subjects who die while on study are considered as having completed the study
Time Definitions (per GSK standard principles)

 • 1 week = 7 days • 1 month = 30.4375 days • 1 year = 365.25 days

